1.3.2.3 Study AC-076-102

This was a randomized, double-blind, placebo-controlled, SAD study to investigate the safety, tolerability, PK, and PD of ACT-246475 after s.c. (Part A) and sublingual (s.l.; Part B) administration to healthy male subjects.

This study has been clinically completed and the database locked. The clinical study report (CSR) is not yet available.

In Part A, there were a total of 48 subjects exposed (6 subjects receiving active treatment and 2 subjects receiving placebo per dose level).

ACT-246475 has been determined to be safe and tolerated at each s.c. dose level ranging from 1 mg to 32 mg.

The overall AE incidence was 12.5% (6 of 48 subjects exposed) with no indication of dose dependency. There were 5 of 36 subjects with AEs after administration of ACT-246475 (13.9%) vs 1 of 12 after placebo (8.3%). Each AE after administration of ACT-246475 was mild and transient.

- In the 2 mg dose group, 2 subjects reported 1 AE each (headache; dizziness) after administration of ACT-246475.
- In the 8 mg dose group, there were 3 subjects with at least 1 AE after administration of ACT-246475 (rhinorrhea; headache; dizziness, nausea and hyperhidrosis).
- One subject reported 3 AEs after administration of placebo (catheter site erythema, nausea, and headache).
- In the other dose groups (1 mg, 4 mg, 16 mg, and 32 mg), no AEs were reported.

There were no deaths, SAEs, bleeding events, or AEs leading to discontinuation of the study. No clinically relevant changes in laboratory variables, vital signs, ECG variables, body weight, physical examination, or vigilance tests were observed.

Peak plasma concentrations were reached within approximately 30–45 min and $t_{1/2}$ ranged from 1.3–9.2 h. Exposure increased in a dose-proportional manner.

At each dose level, peak IPA was achieved within approximately 15–30 min post-dosing. Peak %IPA exceeded 85% at doses ≥ 4 mg. The duration of PD effects was dose dependent. Mean %IPA $\geq 85\%$ was sustained for approximately 6 h and 12 h post-administration of 16 mg or 32 mg ACT-246475, respectively.

In Part B, there were a total of 8 subjects exposed (6/2 on active/placebo). ACT-246475 has been determined to be safe and tolerated after a single s.l. dose of 20 mg. Two subjects reported AEs after s.l. administration of ACT-246475: lightheadedness in 1 subject and headache, vomiting, dizziness, and dyspepsia in the other subject. Neither of the 2 subjects exposed to placebo reported AEs.

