5 TREATMENTS

5.1 Study treatment

5.1.1 Investigational treatment and matching placebo: Description and rationale

Study treatment for s.c. administration will be available as sealed glass vials in 1 strength: 20 mg. The vials contain 22 mg of lyophilized ACT-246475A (hydrochloride salt of

ACT-246475) or matching placebo to be reconstituted with 1 mL of water for injection. The s.c. formulation contains mannitol as an inactive ingredient.

Study treatment will be given as a single dose, administered s.c. at site by qualified personnel (e.g., nurse, physician).

ACT-246475 at 2 different doses (8 and 16 mg) and placebo will be administered during this study. The ACT-246475 doses have been selected based on data from the SAD AC-076-102 study and on modeling to meet the following criteria:

- The low dose (8 mg) is the minimal dose achieving at least 85% IPA for 3 h which corresponds to a time period during which complete suppression of platelet reactivity is needed before specific in-hospital management of ACS [Montalescot 2014].
- The high dose (16 mg) provides IPA of at least 85% in no more than 5% of the subjects at 8 h. This corresponds to the maximal time accepted to limit interference with invasive and/or pharmacological standard of care of AMI.

These 2 doses are considered distinct enough to allow further modeling of the optimal phase 3 dose based on study data.

Note: onset of action of ACT-246475 is not dose-dependent and therefore did not account for dose selection.

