10.3.2.3 Main analysis

The primary statistical analysis will be performed on the FAS population for each dose level.

The first set of null hypotheses (H_{p0HD} and H_{p0LD}) will be tested for each dose by a 2-sided z-test at an overall significance level (alpha) of 0.05 adjusted for multiplicity using the Bonferroni method, i.e., 0.025 for each comparison.

The second null hypothesis (H_0) will be tested for each dose by a 1-sided z-test. The estimated proportion of responders in each arm and the corresponding 95% CI will be provided.

A longitudinal analysis of the treatment effect, from start of treatment up to 8 h after injection, on platelet reactivity as measured by VerifyNow®, i.e., PRU value, will be performed using a mixed model with PRU as the dependent variable, subject as a random factor, and treatment (8 mg, 16 mg, and placebo), injection site (abdomen, thigh), PRU level at randomization (stratification levels), age (continuous), gender (male, female), and assessment time (continuous) as fixed factors. The model will also include (treatment \times injection site) as an interaction term to assess consistency of treatment effect across injection sites.

A logistic regression analysis of the PD response will be performed using the same factor as covariates.

Summary of PD response, in terms of number (%) of subjects, will be provided. IPA as measured by VerifyNow® will also be summarized as a continuous parameter.

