6.8.1 Primary pharmacodynamic endpoint

6.8.1.1 Variable

The primary PD endpoint is the *PD response* that is defined for each subject as a PRU < 100 starting 30 min after injection and lasting for at least 3 h, as measured via VerifyNow®.

The primary PD variable is the platelet reactivity as measured by VerifyNow® at each time point [see tables of assessments in the protocol: table 2 and table 3].

The analysis variable of the PD response is defined as follows for a given subject:

IF maximum of (PRU_{30m}, PRU_{1h}, PRU_{2h}, PRU_{4h}) < 100

AND (no more than 1 intermediate value (PRU_{1h} or PRU_{2h}) missing)

THEN PD response = YES

ELSE PD response = NO

Where PRU_{30m}, PRU_{1h}, PRU_{2h}, and PRU_{4h} refer to PRU measured by VerifyNow® at 30 minutes, 1, 2 and 4 hours after study drug administration. Time is based on planned time point and not on the actual collection time.

Supportive primary PD endpoint estimands

To assess robustness of results, two additional PD endpoints (estimands) will be defined for sensitivity analysis. The first endpoint, noted PD response[#], will be based on the same

algorithm as described above but using the actual collection time to define the following time windows:

Table 4 Time windows definitions

Collection time point (nominal) (time post study drug administration)	Time from PRU _{30m} (assessment of response, i.e., PRU < 100)	Time windows (~ 5% margin) (min. from study drug administration)
15 minutes	-	14 to 16
30 minutes	0	28 to 32
1 hour	30 minutes	57 to 63
2 hours	1.5 hours	114 to 126
3.5 hours*	3 hours	199 to 221
4 hours	3.5 hours	228 to 252
8 hours	7.5 hours	456 to 504
24 hours	23.5 hours	1368 to 1512

* no blood sample is taken at that time point, therefore no PRU value reported.
PRU, P2Y₁₂ reaction units.

The second endpoint, in the event of frequently missing PRU_{1h} or PRU_{2h} values, $\geq 10\%$ missing values overall, noted PD response*, will consider only the 30 minutes and 4 hours post study drug administration time points:

*IF maximum of (PRU_{30m}, PRU_{4h}) < 100
AND none of those values is missing
THEN PD response* = YES
ELSE PD response* = NO*

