The estimated proportion of responders and the corresponding 95% CI will be provided overall and by injection site, for each treatment arm.

A logistic regression analysis of the PD response will be performed to test for treatment effect (8 mg, 16 mg, and placebo) using the following covariates: injection site (abdomen, thigh), PRU level at randomization (stratification levels), age (continuous), sex (male, female), and assessment time (minutes) as continuous.

A longitudinal analysis of the treatment effect, from start of treatment up to 8 hours after injection, on platelet reactivity as measured by VerifyNow®, i.e., PRU value, will be performed using a mixed model with PRU as the dependent variable, subject as a random factor, and treatment (8 mg, 16 mg, and placebo), injection site (abdomen, thigh), PRU level at randomization (stratification levels), age (continuous), sex (male, female), and assessment time (minutes) as fixed factors. The model will also include

(treatment \times injection site) as an interaction term to assess consistency of treatment effect across injection sites.

IPA as measured by VerifyNow® will also be summarized at each time point as a continuous parameter.

The evolution of PRU values over time will be described using box-and-whisker plots, visualizing mean, median, interquartile ranges, SD, and outliers.

Assuming a treatment \times injection site interaction, summary and graphical analyses described above will be repeated by site injection sub-group.

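### The longitudinal PRU model has no treatment-by-time term, so it holds each dose's effect constant from 15 min to 8 h; the PD-response logistic model lists an assessment-time covariate with no defined value

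*SAP*

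**What the plan says.** **Longitudinal model.** SAP 6.8.1.2 models PRU from start of treatment to 8 h with subject as a random factor. The fixed effects are treatment (8 mg, 16 mg, placebo), injection site, PRU stratum and then "age (continuous), sex (male, female), and assessment time (minutes) as fixed factors". One interaction is named, treatment by injection site. Protocol 10.3.2.3 lists the same terms, closing with "gender (male, female), and assessment time (continuous) as fixed factors". SAP 6.8.2.2 applies the same factors to extent of aggregation, absolute PRU, IPA and FPA.

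**Logistic model.** The covariates for PD response in SAP 6.8.1.2 end with "age (continuous), sex (male, female), and assessment time (minutes) as continuous". The probable source is Protocol 10.3.2.3, directly after the mixed model: "A logistic regression analysis of the PD response will be performed using the same factor as covariates". SAP 6.8.1.3 repeats the analysis on PD response# and PD response*.

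**What these models describe.** SAP 6.8.1.1 states: "The primary PD variable is the platelet reactivity as measured by VerifyNow® at each time point". PD response is one yes/no value per subject, from PRU at 30 min and 1, 2 and 4 h, and "Time is based on planned time point and not on the actual collection time".

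**The concern.** The documents expect the two doses to differ in their time course. For the earlier healthy-subject study, Protocol 1.3.2.3 reports: "The duration of PD effects was dose dependent". Protocol 5.1.1 adds that onset does not depend on dose. The curves should therefore agree early and separate late. A model with a single effect per dose cannot show that pattern. It spreads a late difference over all the sampled times.

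At stake is a pre-specified, covariate-adjusted estimate, with an interval, of when and by how much each dose separates from placebo and from the other dose. Protocol 1.4 calls the study's data critical for dose selection.

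The logistic model has a smaller defect. As written it cannot be run until the programmer chooses, undocumented, which time to enter.

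**Working it through.** The plan states no figure to reproduce here. The check concerns model structure, followed by an illustration.

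**1. What the mixed model estimates.** For subject i in arm a, injection site s, at time t:

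E(PRU) = μ + τ_a + σ_s + (τσ)_as + stratum + age + sex + β·t

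The dose-minus-placebo difference within site s is [τ_a + (τσ)_as] − [τ_placebo + (τσ)_placebo,s]. The β·t term cancels, so the difference does not involve t. If time is coded as a factor (β·t replaced by γ_t), γ_t cancels in the same way. The result does not depend on whether SAP assessment time in minutes is read as continuous or categorical.

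When every subject has the same six post-dose VerifyNow times (Protocol Table 3: 15 and 30 min, 1, 2, 4, 8 h), the estimated effect is the unweighted mean of the six time-specific differences. Three of those six samples fall in the first hour, so this is an average over the sampling schedule, not over clock time.

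**2. Illustration.** These profiles are assumed, not trial data (percent inhibition versus placebo):

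| | 15 min | 30 min | 1 h | 2 h | 4 h | 8 h | Mean = model effect |
|---|---|---|---|---|---|---|---|
| 8 mg | 85 | 90 | 90 | 90 | 75 | 30 | 460/6 = 76.7 |
| 16 mg | 85 | 90 | 90 | 90 | 88 | 60 | 503/6 = 83.8 |
| Gap | 0 | 0 | 0 | 0 | 13 | 30 | 43/6 = 7.2 |

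The model reports 7.2 at every time. With no gap up to 2 h, model gap ÷ 8 h gap = (1 + r)/6, where r is the 4 h gap divided by the 8 h gap:

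- r = 0: 1/6 = 17%
- r = 13/30 = 0.43: 24%
- r = 1: 2/6 = 33%

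**3. Check by fitting.** A mixed model with treatment by site, linear time and a random subject effect (stratum, age and sex left out) was fitted to one simulated data set, 108 per arm, under different assumed PRU profiles.

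- 8 mg effect: −133.3 (abdomen) and −129.8 (thigh), against a mean by-time contrast of −131.5.
- 16 mg effect: −148.2 and −146.1, against −147.0.
- 16 mg minus 8 mg: about −15 PRU at every time from the model. The by-time contrasts give −177 − (−183) = +6 at 30 min, −168 − (−112) = −56 at 4 h and −64 − (−10) = −54 at 8 h.

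**4. Logistic covariate.** PD response uses planned times, which are the same for every subject, so a planned time is a constant. The design has 9 columns (intercept, 2 treatment, 1 site, 2 stratum, age, sex, time) and rank 8: time is aliased with the intercept. Protocol 7.2.3.1.1 has actual clock times recorded, but a subject has four of them for this endpoint and neither document says which to use. SAP 11.3 gives no clarification. The SAP's own logistic model for 8 h status (6.8.2.2) has no time term.

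**The case against.** The strongest reply is that little is lost. Absolute PRU at each measured time is a listed endpoint (SAP 6.8.2.1). Summaries by time point are planned, with a 95% CI of the mean when relevant (6.8, 6.8.2.2), as are box plots (6.8.1.2) and a between-arm model of binary 8 h status (6.8.2.2). An unadjusted difference at each time can be derived from the reported N, mean and SD. Protocol 5.1.1 also foresees further dose modeling. All of this stands and limits the point. What is missing is the adjusted, pre-specified contrast by time.

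Some stronger readings are tempting but not supported:

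- **No between-arm comparison at all.** The model does give one. It is held constant over time.
- **The pre-dose sample is an outcome record and dilutes the effect further.** The model runs from start of treatment. SAP 2.3, 10.2.2 and 10.2.4 place the pre-dose sample before that, as baseline.
- **The logistic model will use several rows per subject and inflate type I error.** SAP 6.8.1.1 defines PD response once per subject, and nothing suggests stacked rows. On more natural readings the effect is slight. A constant is redundant, and in one simulated set entering the actual 4 h time moved the two dose odds ratios only from 4.41 to 4.44 and from 3.48 to 3.49.
- **The dose criteria require this model.** Protocol 5.1.1 says "The high dose (16 mg) provides IPA of at least 85% in no more than 5% of the subjects at 8 h". That is a proportion used to select doses from earlier data. Mean PRU contrasts would not test it, and the 8 h status analysis is closer.
- **The covariance must take one particular form.** SAP 6.8.1.2 names a random subject factor and states no residual structure. How far variance differs by arm is not known from the documents.

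**Conclusion.** The point holds on both parts. The longitudinal model, and its reuse in SAP 6.8.2.2, constrains each dose's effect within injection site to be constant over time, against the time course the protocol itself expects. The PD-response logistic model carries a covariate with no defined value.

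The structural result needs no assumption about the data. Its exact form as a simple mean assumes complete, common sampling times, and missing samples would make it approximate. The size is illustrative only. If the doses do not differ before 4 h and the 4 h gap lies between zero and the 8 h gap, the model shows 17% to 33% of the 8 h gap; other profiles give other ratios.

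The primary z-tests, the decision rule and the sample size are unaffected. This is a correction that should be made to supportive models, and for the logistic model it is mainly a matter of wording.

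**What to change.** **Mixed model (SAP 6.8.1.2).** Enter planned post-dose time (15 and 30 min, 1, 2, 4, 8 h) as a categorical factor, add treatment by time, and keep treatment by injection site. Report 8 mg versus placebo, 16 mg versus placebo and 16 mg versus 8 mg with 95% CI at each time, labelled descriptive, plus the time-averaged contrast from the same fit. Use the same form for the longitudinal outcomes in SAP 6.8.2.2, at their own sampled times.

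**Logistic model.** Delete assessment time for PD response and for its repeats on PD response# and PD response* (SAP 6.8.1.3).

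**Optional.** PRU variance may differ by arm and time. A covariance structure or robust standard errors that allow for this would be sensible; the choice is the trial statistician's.

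**Cost.** One time parameter becomes 5 for time plus 10 for treatment by time, so 14 more fixed-effect parameters. With six times there are 3 × 6 = 18 descriptive intervals per outcome. Any injection-site difference in effect would still be held constant over time. No new data are needed.

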3 OVERALL STUDY DESIGN AND PLAN

3.1 Study design

This is a prospective, multi-national, multi-center, double-blind, randomized, placebo-controlled, parallel-group, Phase 2, exploratory study of a single s.c. administration of ACT-246475, at 2 different dose levels, in subjects with stable CAD receiving conventional background therapy (e.g., acetylsalicylic acid, P2Y₁₂ receptor antagonists, etc.).

Approximately 324 adult subjects with stable CAD will be randomized into 1 of the 8 combinations of the treatment, dose, and injection site using a 2:2:2:2:1:1:1:1 ratio as described in [Figure 1](#).

Figure 1 Randomization scheme

Each subject will receive a single s.c. administration of either 8 mg ACT-246475, 16 mg ACT-246475 or matching placebo, either in the thigh or in the abdomen.

Treatment group allocation will be stratified based on baseline platelet reactivity value (expressed as P2Y₁₂ reaction units [PRU]) measured on Day 1 by the VerifyNow® assay before ACT-246475 injection, considering the 3 following categories: high reactivity (PRU > 250), medium reactivity (150 ≤ PRU ≤ 250), and low reactivity (PRU < 150).

No interim analysis is planned for this study.

The study will be conducted at approximately 20 sites and in 5–10 countries (recruitment will be competitive across sites). The list of sites including the name and title of the investigators who are responsible for conducting the trial, and the address and telephone numbers of the trial sites will be filed in the Trial Master File (TMF).

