10.5 Sample size

The sample size is based on the primary PD endpoint, which is the proportion of subjects achieving a predefined PD response as measured by VerifyNow®. The computation of the sample size was performed using the East 6.0 software (version 6.4.0.1, 30 Aug. 2016) from Cytel.

This study includes 3 treatment arms, 2 active arms (ACT-246475 8 mg and 16 mg) and a placebo arm comprising the 2 dose-matching placebo groups.

The primary objective is to assess the effectiveness of ACT-246475 to allow subjects to achieve a predefined PD response, therefore the sample size will be provided in order to reach the necessary power to sequentially demonstrate that at least 1 of the 2 doses has a higher response rate than placebo and that this response rate is statistically significantly greater than the proportion of responders under H_0 .

The sample size required for demonstrating a difference to placebo is based on an overall alpha of 0.05 (2-sided), adjusted for multiplicity using a Bonferroni method to 0.025 for each comparison, and a power of 0.9; the assumptions related to response rate under the null and alternative hypotheses are reported in the table below:

Proportion of responders under H_0 (placebo)	Proportion of responders under H_1 (active)	Number of subjects (total)	Number of subjects (per arm)
50%	75% (odds ratio of 3)	288	96

The sample size required to demonstrate that the achieved response rate is different from 70% is based on a 2-sided type I error (alpha) of 0.025, and a power of 0.9; the assumptions related to response rate under the null and alternative hypotheses, are reported in the table below:

Proportion of responders under H_0	Proportion of responders under H_1	Number of subjects (total for the 2 active arms)	Number of subjects (per arm)
70%	85%	196	98

Therefore the study should include at least 98 subjects evaluable for the primary PD endpoint in each treatment arm. Assuming a rate of drop-out or non-evaluable data of about 10%, each arm will include 108 subjects leading to a total for the study of 324 subjects.

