3.3 Other objectives

The other objectives of this study, following a single s.c. administration of ACT-246475, are:

- To assess the pharmacokinetics (PK) of ACT-246475.
- To assess the impact of the injection site location (thigh vs abdomen) on the PK and pharmacodynamics (PD) of ACT-246475.
- To investigate the impact of concomitant drug use, age, sex, and other covariates on the PK and PD of ACT-246475.
- To investigate the safety and tolerability of ACT-246475.

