6.8.2.2 Analyses

Summary statistics will be provided for all secondary PD endpoints variables, by time point, and individual data will be listed.

The variables' extent of aggregation, absolute PRU, IPA, and FPA will be analyzed similarly to the longitudinal analysis described for the primary PD endpoint in Section 6.8.1.2, and will use the same factors.

A logistics regression model will be used to assess the treatment effect relative to placebo of each ACT-246475 dose on subject platelet aggregation status 8 hours after study drug administration. The factor considered in addition to the treatment group, will include injection site (abdomen, thigh), PRU level at randomization (stratification levels), age (continuous), and sex (male, female) as fixed factors. The model will also include (treatment \times injection site) as an interaction term to assess consistency of treatment effect across injection sites.

Proportion of subject by platelet aggregation status 8 hours after study drug administration will be plotted as bar charts. Additional graphs will be provided by injection site.

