8.1.1 Treatment groups

The study included the following 8 *randomization groups* corresponding to the combination of the four study treatment groups (i.e., ACT-246475 8 mg, ACT-246475 16 mg, and their matching placebos) and two injection sites (thigh and abdomen).

The main purpose of this randomization strategy was to balance treatment as well as site of injection assignment. For the analysis, the study treatment arms will consist of the treatment arms: *Placebo*, *ACT-246475 8 mg*, and *ACT-246475 16 mg*. The placebo treatment arm combines the two placebo dose-matching groups.

All analyses, unless stated otherwise, will be reported by those 3 treatment arms, and in this order.

In all Tables, Figures and Listings, treatment groups will be labeled using treatment label [last column of [Table 6](#)].

Table 6 Randomization groups and treatment group labels

Randomization groups		Treatment groups (labels for outputs)
Treatment	Injection site	
ACT-246475 8 mg	Thigh	ACT-246475 8 mg
ACT-246475 8 mg	Abdomen	
ACT-246475 16 mg	Thigh	ACT-246475 16 mg
ACT-246475 16 mg	Abdomen	
Placebo matching ACT-246475 8 mg	Thigh	Placebo
Placebo matching ACT-246475 8 mg	Abdomen	
Placebo matching ACT-246475 16 mg	Thigh	
Placebo matching ACT-246475 16 mg	Abdomen	

Some analyses may require displaying some of the following groups: *Screened failure* subjects group, *Total randomized* (i.e., any subject who has been assigned a study treatment), *Total ACT-246475* group (i.e., subjects randomized to either ACT-246475 8 or 16 mg arms), and *Total* (i.e., all subjects screened).

The order of the treatment group in the statistical report, would then be: Screened failures, ACT-246475 8 mg, ACT-246475 16 mg, Total randomized, Total ACT-246475, and Total.

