13 APPENDICES

Appendix A Protocol synopsis

PROTOCOL SYNOPSIS ID-076A201

TITLE	A multi-center, double-blind, randomized, placebo-controlled study to assess the pharmacodynamics, pharmacokinetics, tolerability, and safety of a single subcutaneous injection of ACT-246475 in adults with stable coronary artery disease.
OBJECTIVES	Primary objective(s) The primary objective of the study is to characterize inhibition of platelet aggregation (IPA) relatively to placebo after a single subcutaneous (s.c.) injection of ACT-246475 either in the thigh or in the abdomen at 2 different doses in subjects with stable coronary artery disease (CAD) receiving conventional background oral antiplatelet therapy (e.g., acetylsalicylic acid, P2Y ₁₂ receptor antagonists). Other objectives The other objectives of this study are described in Section 2.2.
DESIGN	This is a prospective, multi-national, multi-center, double-blind, randomized, placebo-controlled, parallel-group, Phase 2, exploratory study of a single s.c. administration of ACT-246475, at 2 different dose levels, in subjects with stable CAD receiving conventional background therapy (e.g., acetylsalicylic acid, P2Y ₁₂ receptor antagonists, etc.). Approximately 324 adult subjects with stable CAD will be randomized into 1 of the 8 combinations of the treatment, dose, and injection site using a 2:2:2:2:1:1:1:1 ratio:

	<pre> graph TD Randomization[Randomization] --> ACT[ACT-246475] Randomization --> Placebo[Placebo] ACT --> 8mg[8 mg] ACT --> 16mg[16 mg] Placebo --> 8mg[8 mg] Placebo --> 16mg[16 mg] 8mg --> Thigh1[Injection: Thigh] 8mg --> Abdomen1[Injection: Abdomen] 16mg --> Thigh2[Injection: Thigh] 16mg --> Abdomen2[Injection: Abdomen] 8mg --> Thigh3[Injection: Thigh] 8mg --> Abdomen3[Injection: Abdomen] 16mg --> Thigh4[Injection: Thigh] 16mg --> Abdomen4[Injection: Abdomen] Thigh1[54 subjects] Abdomen1[54 subjects] Thigh2[54 subjects] Abdomen2[54 subjects] Thigh3[27 subjects] Abdomen3[27 subjects] Thigh4[27 subjects] Abdomen4[27 subjects] </pre>

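### Site consistency in the PRU and 8 h models rests on a treatment × injection-site term; no thigh-minus-abdomen difference on drug, with its interval, is planned

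*SAP*

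**What the plan says.** SAP 3.3 lists among the other objectives: "To assess the impact of the injection site location (thigh vs abdomen") on PK and PD. Protocol 2.2 has the same objective. Site is part of the randomisation: subjects are "randomized into 1 of the 8 combinations of the treatment, dose, and injection site using a 2:2:2:2:1:1:1:1 ratio" (Protocol 3.1).

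Two models carry a treatment × injection-site term:

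- **Longitudinal PRU mixed model** (SAP 6.8.1.2, Protocol 10.3.2.3). The term is there "as an interaction term to assess consistency of treatment effect across injection sites".
- **Logistic model for platelet aggregation status at 8 h** (SAP 6.8.2.2). The term is included for the same purpose.

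Neither section gives a significance level, a decision rule, a confidence interval for the interaction or a site difference of interest. SAP 6.8.1.2 then says that, if a treatment × site interaction is assumed, "summary and graphical analyses described above will be repeated by site injection sub-group".

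Some by-site reporting does not depend on an interaction:

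- responder proportions with 95% CI by site and arm (6.8.1.2);
- bar charts of 8 h status by site (6.8.2.2);
- descriptive statistics by site for the secondary PD endpoints (6.8.2.4). The natural reading is the endpoints listed in 6.8.2.1, which include absolute PRU. SAP 6.8 adds a 95% CI of the mean where relevant.

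**The concern.** The objective asks how far thigh and abdomen differ in PD and what difference the data exclude. That calls for an estimate with an interval. The two models instead look for an interaction, and the sample size (Protocol 10.5) covers only the responder tests. If no interaction appears, the models as specified say nothing about how large a site difference remains compatible with the data.

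The interaction is also an imprecise tool for this question. It subtracts the site difference on placebo from the site difference on drug. Injection site cannot change a drug effect in subjects who received no drug, so the subtraction mainly adds variance.

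The drug is being developed for self-injection (Protocol 1.1), so a usable statement about the two sites has practical value.

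**Working it through.** **1. The plan's own figures.** Protocol 10.5 gives 96 and 98 per arm, then says "each arm will include 108 subjects leading to a total for the study of 324 subjects".

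- 50% vs 75%, two-sided 0.025, power 0.90, log odds ratio formula: (2.241 + 1.282)² × [1/(0.5×0.5) + 1/(0.75×0.25)] / (ln 3)² = 95.98, so 96.
- 70% vs 85%, one sample, two-sided 0.025, power 0.90: (2.241×√0.21 + 1.282×√0.1275)² / 0.15² = 97.98, so 98.
- 98 × 1.1 = 107.8, so 108; 3 × 108 = 324.

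The figures reproduce. None of them concerns injection site.

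**2. Cell sizes.** The ratio sums to 12 and 324/12 = 27. Each active dose-by-site cell therefore has 54 subjects and each placebo dose-by-site cell has 27. SAP 8.1.1 states: "The placebo treatment arm combines the two placebo dose-matching groups". Placebo thus has 27 + 27 = 54 per site. With 98 evaluable per arm, the cell size is n = 49.

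**3. Assumptions (not in the documents).** The site shift is 0.5 SD in both active doses and zero on placebo. The SD is that of the subject-level mean PRU, equal across cells. Alpha is 0.05 two-sided.

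**4. Standard errors in SD units.**

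| Quantity | Formula | n = 54 | n = 49 |
|---|---|---|---|
| Site contrast within one dose | √(2/n) | 0.192 | 0.202 |
| Site contrast averaged over the two doses | √(1/n) | 0.136 | 0.143 |
| Averaged active site contrast minus placebo site contrast | √(1/n + 2/n) = √(3/n) | 0.236 | 0.247 |

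The variance ratio of the last two rows is (3/n)/(1/n) = 3 whatever the SD. At n = 54 the 95% CI half-widths are 1.96 × 0.136 = 0.27 SD and 1.96 × 0.236 = 0.46 SD.

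**5. Power.** For the 2-df interaction test, the noncentrality is (n/2) × Σ(d − mean d)² with d = (0.5, 0.5, 0). This gives 4.50 at n = 54 and 4.08 at n = 49. For the contrasts, power is Φ(δ/SE − 1.96), ignoring the negligible opposite tail.

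| Test, alpha 0.05 | n = 54 | n = 49 |
|---|---|---|
| 2-df interaction | 46% | 42% |
| Averaged interaction contrast (1 df) | 56% | 52% |
| Site contrast within one dose | 74% | 70% |
| Site contrast averaged over doses | 96% | 94% |

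**6. Sensitivity.**

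- *Alpha 0.10:* interaction power is 58–59% (n = 54) or 55% (n = 49).
- *SD of a single-time PRU:* averaging six post-dose times up to 8 h multiplies the variance by (1 + 5ρ)/6, where ρ is the within-subject correlation. At n = 54, interaction power is 84%, 70%, 58% and 49% for ρ = 0.3, 0.5, 0.7 and 0.9. The averaged active contrast has at least 97% in each case.
- *Shift in one dose only:* the averaged contrast sees 0.25 SD. Power is Φ(0.25/0.136 − 1.96) = 45% at n = 54 and 42% at n = 49, no better than the interaction test (46% and 42%). The contrast within the affected dose keeps 74% and 70%.

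No figure is given for 8 h status, because the documents state no 8 h rates. The argument about what is estimated is the same.

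**The case against.** A fair defence has four parts.

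- **By-site results do not disappear when no interaction is seen.** This stands. Responder rates with intervals, absolute PRU descriptives and 8 h graphs by site are planned regardless. A reader might infer that the site question goes unreported without an interaction; the documents do not support that. What these outputs lack is a difference between sites with its uncertainty. The logistic regression of the primary PD response has site as a covariate and names no interaction. It would yield a site odds ratio, but one averaged over placebo as well and not named as an output.
- **The SAP never says that a non-significant interaction will be reported as consistency.** This also stands. It gives no test or cut-off, so a prediction that a moderate difference would be declared consistent goes beyond the text. Detailed outputs are in a separate list (SAP 12), which may contain more. The silence is itself the gap: the term is assigned to judging consistency with no rule for reading it.
- **The power figures rest on outside assumptions.** A reader might conclude that the test misses a 0.5-SD site difference more than half the time. That holds only with alpha 0.05 and the subject-mean SD, and it reverses at alpha 0.10 or with a single-time SD and moderate correlation. The comparison with the averaged contrast also favours that contrast by assuming the same shift in both doses.
- **The interaction answers its own question, and the study is exploratory.** The term is legitimate for consistency of the effect relative to placebo and can stay. Site is an other objective, not the primary one. Both facts limit the weight of the point, but an exploratory aim is better served by estimates than by an unsized interaction term.

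**Conclusion.** The point holds as a free improvement. For the PRU and 8 h status models, the SAP names only an interaction term for site consistency, makes part of the by-site display conditional on it, and plans no thigh-minus-abdomen difference with an interval on drug.

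With equal cells and SD, the averaged active contrast has one third of the variance of the averaged interaction contrast; this does not depend on the assumed effect size. The power gap of 42–46% against 94–96% does depend on it, and on the alpha, the SD definition and an equal shift in both doses. If one dose alone is affected, the averaged contrast has no advantage, so the within-dose contrasts must be shown beside it. The primary responder tests are not touched.

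**What to change.** In SAP 6.8.1.2 (PRU mixed model) and 6.8.2.2 (8 h status model):

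1. Keep both models and the interaction term.
2. Add thigh-minus-abdomen contrasts with 95% CIs within each active dose and averaged over the two doses. For 8 h status, use an odds ratio or risk difference.
3. State that site consistency is read from these intervals, and that a non-significant interaction is not evidence of consistency.
4. In 6.8.1.2, delete the condition on an interaction, so that the by-site summaries and plots are always produced.

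The cost is SAP wording and a few more outputs from models already planned. No new data or subjects are needed.
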